### 1.2 SCHEMA

**Figure 1. Flowchart of screening, inclusion, and assessment process**

### 1.3 SCHEDULE OF ACTIVITIES

	Pre-screening	Visit 1 Day 1	Visit 2 to Visit 11 Day 3 ±1 to Day 30±1	Visit 12 Day 31 ±2	Visit 13 Day 90 ±2
Review Eligibility	X				
Informed Consent		X			
Demographics		X			
Outcome Evaluation					
Brain Assessment (MRI scan)		X		X	X
Cognitive Assessment (Self-control tasks)		X		X	X
Randomization		X			
Control & Experimental Interventions		X	X		
Adverse Events Reporting		X	X	X	X

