#### 9.3 POPULATIONS FOR ANALYSES

*The analysis population will be Modified Intention-to-Treat Analysis Population. Specifically, these participants are those who completed the full-dose of the intervention (10 sessions) and have completed data for the primary endpoint.*

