## 9.4 STATISTICAL ANALYSES PLAN

### 9.4.1 GENERAL APPROACH

*Behavioral and brain data analysis will undergo separate analyzing streams to test intervention effects and underlying mechanisms at baseline and post-intervention. Given the scope of this 2-year R61 project, the logical first step at this early stage of research is to examine the potential intervention effects and mechanisms, then move to the full scale RCTs for R33 phase. To address our study Aims, repeated-measures ANOVA will be used. By utilizing all assessment points, this approach allows for well-powered tests to detect significant differences in changes across the experimental conditions, even when assuming smaller magnitude effect sizes. Effect size measures (from the repeated-measures ANOVA, Cohen's  $d$  highlighting mean differences between treatment and control groups across assessments) will also be calculated to describe the intervention's effect on study outcomes.*

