### 9.4.2 ANALYSIS OF THE PRIMARY ENDPOINT(S)

*The primary endpoints are brain assessments and are all repeated measures assessed at baseline and post-intervention. For brain assessment of brain assessment of functional activity, whole-brain analyses of fMRI timeseries during resting state will be calculated and for all endpoints based on standardized processing pipelines of fMRI data using REST software ([www.restfmri.net](http://www.restfmri.net)). After these data preprocessing and calculation, numerical values will be generated for each brain voxel. Next, the effects of intervention (IBMT vs. RT) on primary endpoints will be examined using repeated-measures ANOVA with time x group interaction effect. Threshold-free cluster enhancement approach will be used to identify clusters showing significant effects. Variance and covariance across repeated measures will be calculated as part of the ANOVA. Age and sex will be included as covariates to control for potential confounding effects of age and sex on brain outcomes. Results will be presented as F values for the interaction effect, along with p values to indicate statistical significance. Normality and homogeneity of variance assumptions will be checked using SPSS built-in tools for ANOVA. Multiple comparison corrections will be conducted using FDR correction. Missing data will be handled with case-wise deletion.*

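### The primary analysis compares change without adjusting for baseline and deletes incomplete cases: it loses precision, and is biased if baseline-related loss differs between arms

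*Combined protocol and SAP*

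**What the plan says.** Section 9.4.2 gives the primary endpoints as brain measures that "are all repeated measures assessed at baseline and post-intervention". The effect of IBMT versus RT "will be examined using repeated-measures ANOVA with time x group interaction effect", and on adjustment the section says: "Age and sex will be included as covariates to control for potential confounding effects of age and sex on brain outcomes". Baseline activity is not a covariate. On missing scans the whole rule is: "Missing data will be handled with case-wise deletion".

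Three other places bear on this.

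- Section 9.3 limits the analysis set: "these participants are those who completed the full-dose of the intervention (10 sessions) and have completed data for the primary endpoint".
- Section 9.4.1 argues for the ANOVA thus: "By utilizing all assessment points, this approach allows for well-powered tests to detect significant differences in changes across the experimental conditions". The schedule in Section 1.3 has three MRI scans (Day 1, Day 31, Day 90), but Section 9.4.2 names only baseline and post-intervention.
- Sections 5.5 and 9.2 plan for 20% loss, so that 56 of 70 complete, or 28 per arm if loss is equal.

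No missing-data assumption, likelihood-based model, imputation or sensitivity analysis is given anywhere.

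**The concern.** With two visits, the time-by-group interaction is the difference between arms in mean change among people with both scans. Change is correlated with baseline: people who start low tend to rise and people who start high tend to fall, whatever the treatment. If the people lost from one arm differ in baseline from those lost from the other, the remaining groups regress by different amounts, and the difference is read as a treatment effect. Randomisation does not protect against this, because the selection comes after it.

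An unadjusted change score is also less precise than an analysis that conditions on baseline whenever the correlation is below 1, which matters with about 28 pairs per arm. Finally, if Section 9.4.1 is taken at its word and Day 90 enters the ANOVA, one missed Day 90 scan deletes a person whose baseline and Day 31 scans are both good.

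**Working it through.** **Inputs.** From Section 9.2: 35 per arm, d = 0.80 between arms at post-intervention, 90% power, up to 20% attrition. From Section 5.5: 56 completers, so 28 per arm. Assumed, because the plan gives no values: two-sided alpha 0.05; equal variance at each visit (SD = 1); correlation r between any two scans of 0.3 to 0.7. All figures are for a single summary value. They ignore voxelwise correction and clustering by training group.

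**1. The plan's own figure.** Power = Φ(d√(n/2) − 1.96).
- n = 35: 0.80 × √17.5 = 3.347, power 91.7% (91.0% by noncentral t). The stated 90% reproduces, with no loss.
- n = 28: 0.80 × √14 = 2.993, power 84.9% (83.6% by t).

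**2. Bias.** Given baseline y0, expected change in an arm is that arm's true mean change plus (r − 1)·y0. Hence

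bias = (r − 1) × (difference between arms in completers' mean baseline).

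Suppose 20% loss in both arms, unrelated to baseline in RT and concentrated in low-baseline people in IBMT (logit slope −1.2 per SD, assumed). IBMT completers' mean baseline is then 0.197 SD above that of everyone randomised.

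| r | Bias (SD) | Share of 0.80 |
|---|---|---|
| 0.3 | −0.7 × 0.197 = −0.14 | 17% |
| 0.5 | −0.5 × 0.197 = −0.10 | 12% |
| 0.7 | −0.3 × 0.197 = −0.06 | 7% |

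A simulation (35 per arm, 20% loss of the post scan, r = 0.5, 6,000 runs per scenario, slopes of size 1 per SD) agrees:
- same dependence in both arms: bias about 0.00;
- one arm only: 0.08;
- opposite directions: 0.18, with type I error 9.7%.

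A likelihood-based mixed model had bias of about 0.00 in all three, and type I error of 4.5% in the last.

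**3. Precision with 28 complete pairs per arm.** Change score: SE = √(4(1 − r)/28). Baseline-adjusted: SE = √(2(1 − r²)/28).

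| r | Change score | Baseline-adjusted |
|---|---|---|
| 0.3 | 0.316 | 0.255 |
| 0.5 | 0.267 | 0.231 |
| 0.7 | 0.207 | 0.191 |

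At r = 0.5 and a true difference of 0.80 SD, power goes from 84.9% to Φ(0.80/0.2315 − 1.96) = Φ(1.50), about 93%.

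**4. What incomplete cases add beyond baseline adjustment.**
- *Only post scans lost* (35 baselines, 28 pairs per arm): the mixed model with a common baseline mean has SE 0.2315 at r = 0.5, exactly that of the complete-case baseline-adjusted analysis. The two also coincide at r = 0.3 and 0.7. Baseline-only people add nothing.
- *Each of two scans lost independently in 10% of 28 per arm* (assumed): 0.81 × 28 = 22.7 pairs remain. At r = 0.5 the SEs are 0.297 (change score), 0.257 (complete-case, baseline-adjusted) and 0.247 (mixed model). The last step is worth (0.257/0.247)² − 1, about 8% effective sample, or 6% to 10% for r = 0.7 to 0.3.
- *Deletion across three scans*: 0.729 × 28 = 20.4 people remain and the change-score SE is 0.313. The mixed model (SE 0.245) then adds 20% to 23% over the complete-case adjusted analysis.

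**5. Loss that depends on the unseen post value.** With opposite directions in the two arms and r = 0.5, bias was −0.17 SD for case-wise deletion and −0.26 SD for the mixed model.

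**The case against.** The strongest reply is that deletion itself does little harm here. A reader might infer that any baseline-related loss biases the arm contrast. It does not: equal dependence cancels, and nothing in the documents indicates that loss will differ by arm. The −1.2 slope is an assumption. Under that mechanism a complete-case analysis adjusted for baseline is also unbiased, so the cause is the unadjusted change score and not the deletion. This stands.

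A reader might also set 0.297 or 0.313 against 0.245 and credit the whole gap to recovered scans. Most of it is baseline adjustment (0.297 to 0.257 of the fall to 0.247 with two scans). The 10% per-scan loss is not in the documents either. It comes on top of a figure of 28 that is already net of 20% attrition, and Section 4.4 counts the baseline and post assessments as part of completion. This stands too.

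Nor does a mixed model cure the problem outright. It relies on missing at random and can do worse otherwise (step 5). Section 9.3 removes people with incomplete data before any model is fitted, and Section 7.1 means that many who discontinue are not scanned again.

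The three-scan case rests on one phrase in Section 9.4.1, against Sections 3, 4.4 and 9.4.2, which all refer to baseline and post-intervention.

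What does not stand is that a new model would have no effect while Section 9.3 is unchanged. Even among complete pairs, conditioning on baseline gains precision and removes bias from baseline-related loss that differs by arm.

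**Conclusion.** The point holds in a limited form, as an inexpensive improvement and not a fatal flaw. The planned contrast is unadjusted for baseline activity. It is open to bias of about 0.06 to 0.14 SD, or 7% to 17% of the planned effect, if 20% loss depends on baseline in one arm only with the assumed slope and r between 0.3 and 0.7. If the dependence is the same in both arms, the bias is about zero. The precision loss does not need any assumption about why people drop out: at r = 0.5 with 28 pairs per arm, the SE is 0.267 SD where 0.231 is available.

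The documents do not support the stronger reading that deletion discards a large amount of usable information. With two visits the extra gain from incomplete cases is nil if only post scans are lost, and 6% to 10% if 10% of each scan is lost. It becomes material only if Day 90 enters the ANOVA, which the plan leaves unclear. The proposed model's protection depends on missing at random.

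**What to change.** In Section 9.4.2, replace the deletion sentence and the primary model with wording such as:

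> The ACC/mPFC summary value (the endpoint of Sections 3 and 9.1) will be analysed with a linear mixed model (unstructured covariance, restricted maximum likelihood) using every available scan, with a common baseline mean, visit and arm-by-visit terms, age and sex. The primary contrast is IBMT minus RT at Day 31. Missing scans are assumed missing at random. Sensitivity analyses: complete pairs only, and an arm-specific shift (delta) applied to missing Day 31 values.

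Companion edits:
- Section 9.3: remove the condition of complete primary-endpoint data. Without this, incomplete cases never reach the model. The ten-session condition is a separate question.
- Sections 9.4.1 and 9.4.2: reconcile which visits enter the primary model, so that a missed Day 90 scan cannot delete a complete baseline and Day 31 pair.
- The voxelwise threshold-free cluster analysis can stay on complete pairs, with its status relative to the summary analysis stated.

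If only one change is made, adding baseline activity to the complete-case analysis captures most of the gain.

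Cost: the plan has no region summary, so one must be defined before the data are seen, and making it the basis of the primary contrast is more than a wording change. The model itself is standard and adds slightly to the analysis work. Scans not taken under Section 7.1 are not recovered by any of this.

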### 9.4.3 ANALYSIS OF THE SECONDARY ENDPOINT(S)

N/A

### 9.4.4 SAFETY ANALYSES

N/A

### 9.4.5 BASELINE DESCRIPTIVE STATISTICS

*Intervention groups will be compared on baseline characteristics including demographics and behavioral assessments of polysubstance use using independent samples t-tests.*

### 9.4.6 PLANNED INTERIM ANALYSES

N/A

#### 9.4.7 SUB-GROUP ANALYSES

*Sub-group analyses will not be conducted for primary and secondary outcomes for this pilot study, as the sample size of sub-groups (N<10) based on age, sex, race/ethnicity or other demographic characteristic(s) will not be sufficient to conduct meaningful group analyses.*

#### 9.4.8 TABULATION OF INDIVIDUAL PARTICIPANT DATA

*Individual participant data will not be tabulated as the goal of the study is to examine group effects.*

#### 9.4.9 EXPLORATORY ANALYSES

*N/A*

### 10 SUPPORTING DOCUMENTATION AND OPERATIONAL CONSIDERATIONS

#### 10.1 REGULATORY, ETHICAL, AND STUDY OVERSIGHT CONSIDERATIONS

##### 10.1.1 INFORMED CONSENT PROCESS

###### 10.1.1.1 CONSENT/ASSENT AND OTHER INFORMATIONAL DOCUMENTS PROVIDED TO PARTICIPANTS

Consent forms describing in detail the study intervention, study procedures, and risks will be given to the participant and written documentation of informed consent will be completed prior to starting the study intervention. The following consent materials are submitted with this protocol: 1. Consent Form.

###### 10.1.1.2 CONSENT PROCEDURES AND DOCUMENTATION

*Informed consent will be administered by a member of the study team to the participant. The team member will give the participant a brief overview of the consent form and summarize relevant information from each section of the consent form. Participants will then be given time to read the consent form on their own. The study population involves English speaking cognitively normal adults, so no special procedures are needed to obtaining the consent. Participants will be asked if they understand and comprehend the consent form and if they have any questions. These procedures serve as means for determining competency and assessing comprehension/understanding of the participants. Any questions the participants may have will be answered by the team member. Finally, participants are asked to indicate if they would like to enroll in the study or not by signing or not signing the consent form.*

###### 10.1.2 STUDY DISCONTINUATION AND CLOSURE

This study may be temporarily suspended or prematurely terminated if there is sufficient reasonable cause. Written notification, documenting the reason for study suspension or termination, will be provided

by the suspending or terminating party to study participants, funding agency, and regulatory authorities. If the study is prematurely terminated or suspended, the Principal Investigator (PI) will promptly inform study participants, the Institutional Review Board (IRB), and sponsor/funding agency and will provide the reason(s) for the termination or suspension. Study participants will be contacted, as applicable, and be informed of changes to study visit schedule.

Circumstances that may warrant termination or suspension include, but are not limited to:

- Determination of unexpected, significant, or unacceptable risk to participants
- Insufficient compliance of study staff to the protocol (ie, significant protocol violations)
- Pandemic, such as COVID-19

The study may resume once concerns about safety, protocol compliance, and data quality are addressed, and satisfy the funding agency, sponsor, IRB, Food and Drug Administration (FDA), or other relevant regulatory or oversight bodies (OHRP, DSMB).

---

#### 10.1.3 CONFIDENTIALITY AND PRIVACY

Participant confidentiality and privacy is strictly held in trust by the participating investigators, their staff, the safety and oversight monitor(s), and the sponsor(s) and funding agency. This confidentiality is extended to the data being collected as part of this study. Data that could be used to identify a specific study participant will be held in strict confidence within the research team. No personally-identifiable information from the study will be released to any unauthorized third party without prior written approval of the sponsor/funding agency.

All research activities will be conducted in as private a setting as possible.

The study monitor, other authorized representatives of the sponsor or funding agency, representatives of the Institutional Review Board (IRB), regulatory agencies, may inspect all documents and records required to be maintained by the investigator. The study site will permit access to such records.

The study participant's contact information will be securely stored at the study site for internal use during the study. At the end of the study, all records will continue to be kept in a secure location for as long a period as dictated by the reviewing IRB, Institutional policies, or sponsor/funding agency requirements.

#### Measures Taken to Ensure Confidentiality of Data Shared per the NIH Data Sharing Policies

It is NIH policy that the results and accomplishments of the activities that it funds should be made available to the public (see <https://grants.nih.gov/policy/sharing.htm>). The PI will ensure all mechanisms used to share data will include proper plans and safeguards for the protection of privacy, confidentiality, and security for data dissemination and reuse (e.g., all data will be thoroughly de-identified and will not be traceable to a specific study participant). Plans for archiving and long-term preservation of the data will be implemented, as appropriate.

#### Certificate of Confidentiality

To further protect the privacy of study participants, the Secretary, Health and Human Services (HHS), has issued a Certificate of Confidentiality (CoC) to all researchers engaged in biomedical, behavioral, clinical or other human subjects research funded wholly or in part by the federal government. Recipients of NIH funding for human subjects research are required to protect identifiable research information from forced disclosure per the terms of the NIH Policy (see <https://humansubjects.nih.gov/coc/index>). As set forth in 45 CFR Part 75.303(a) and NIHGPS Chapter 8.3, recipients conducting NIH-supported research covered by this Policy are required to establish and maintain effective internal controls (e.g., policies and procedures) that provide reasonable assurance that the award is managed in compliance with Federal statutes, regulations, and the terms and conditions of award. It is the NIH policy that investigators and others who have access to research records will not disclose identifying information except when the participant consents or in certain instances when federal, state, or local law or regulation requires disclosure. NIH expects investigators to inform research participants of the protections and the limits to protections provided by a Certificate issued by this Policy.

---

#### 10.1.4 FUTURE USE OF STORED SPECIMENS AND DATA

Data collected for this study will be analyzed and stored at the study site. After the study is completed, the de-identified, archived data will be transmitted to and stored at the study site's secured data storage space. The use of the de-identified data by other researchers including those outside of the study will be granted per reasonable requests.

---

#### 10.1.6 SAFETY OVERSIGHT

Safety oversight will be under the direction of a Data and Safety Monitoring Board (DSMB) composed of individuals with the appropriate expertise, including clinical trials and intervention. Members of the DSMB will be independent from the study conduct and free of conflict of interest. The DSMB will meet at least semiannually to assess safety and efficacy data from each arm of the study. The DSMB will operate under the rules of an approved charter that will be written and reviewed at the organizational meeting of the DSMB. At this time, each data element that the DSMB needs to assess will be clearly defined. The DSMB will provide its input to NCCIH via annual report.

---

#### 10.1.7 CLINICAL MONITORING

Clinical site monitoring will be conducted to ensure that the rights and well-being of trial participants are protected, that the reported trial data are accurate, complete, and verifiable, and that the conduct of the trial is in compliance with the currently approved protocol/amendment(s), with International Council on Harmonisation Good Clinical Practice (ICH GCP), and with applicable regulatory requirement(s). Monitoring activities will be conducted by the study site itself, so please see **Section 10.1.8, Quality Assurance and Quality Control.**

---

#### 10.1.8 QUALITY ASSURANCE AND QUALITY CONTROL

The study site will perform internal quality management of study conduct, data collection, documentation and completion. Quality control (QC) procedures will be implemented as follows:

**Informed consent** --- Study staff will review both the documentation of the consenting process as well as a percentage of the completed consent documents. This review will evaluate compliance with GCP, accuracy, and completeness. Feedback will be provided to the study team to ensure proper consenting procedures are followed.

**Source documents and the electronic data** --- Data will be initially captured on source documents (see **Section 10.1.9, Data Handling and Record Keeping**) and will ultimately be entered into the study database. To ensure accuracy site staff will compare a representative sample of source data against the database, targeting key data points in that review.

**Intervention Fidelity** — Consistent delivery of the study interventions will be monitored throughout the intervention phase of the study. Procedures for ensuring fidelity of intervention delivery are described in **Section 6.2.1, Interventionist Training and Tracking**.

**Protocol Deviations** – The study team will review protocol deviations on an ongoing basis and will implement corrective actions when the quantity or nature of deviations are deemed to be at a level of concern.

Should independent monitoring become necessary, the PI will provide direct access to all trial related sites, source data/documents, and reports for the purpose of monitoring and auditing by the sponsor/funding agency, and inspection by local and regulatory authorities.

---

#### 10.1.9 DATA HANDLING AND RECORD KEEPING

---

##### 10.1.9.1 DATA COLLECTION AND MANAGEMENT RESPONSIBILITIES

Data collection will be the responsibility of study team at the site under the supervision of the site investigator. The investigator will be responsible for ensuring the accuracy, completeness, legibility, and timeliness of the data reported.

All source documents will be completed in a neat, legible manner to ensure accurate interpretation of data.

Hardcopies of the study visit worksheets will be provided for use as source document worksheets for recording data for each participant consented/enrolled in the study. Data recorded in the electronic case report form (eCRF) derived from source documents will be consistent with the data recorded on the source documents.

Clinical data (including adverse events (AEs) and SAEs will be entered into RedCap provided by the study site. The data system includes password protection and internal quality checks, such as automatic range checks, to identify data that appear inconsistent, incomplete, or inaccurate. Clinical data will be entered directly from the source documents.

---

